21.3.3 Disease Activity Score 28 (DAS28)

The DAS28 is a combined index for measuring disease activity in RA. The index includes swollen and tender joint counts, CRP, and general health status. In this trial CRP will be used to calculate the DAS28 score. The index is calculated using the following formula:

DAS28-CRP(4) = 0.56*sqrt(TJC28) + 0.28*sqrt(SJC28) + 0.36*ln(CRP+1) + 0.014*GH + 0.96

Where, TJC = tender joint count on 28 joints, SJC = swollen joint count on 28 joints, In = natural log, CRP = C-reactive Protein, and GH = general health, i.e., patient's global assessment of disease activity (100-mm VAS).

The DAS28 provides an absolute indication of RA disease activity on a scale of 0.49 to 9.07

- A DAS28 value >5.1 corresponds to a high disease activity
- A DAS28 value between 3.2 and 5.1 corresponds to a moderate disease activity
- A DAS28 value between 2.6 and 3.2 corresponds to a low disease activity
- A DAS28 value < 2.6 corresponds to remission

Compared to an initial value the disease activity of the subject can be classified as follows:

Current DAS28		DAS28 decrease from initial value				
		>1.2	> 0.6 but ≤ 1.2	≤ 0.6		
≤ 3.2 Inactive		Good improvement	Moderate improvement	No improvement		
>3.2 but ≤ 5.1 Moderate		Moderate improvement	Moderate improvement	No improvement		
> 5.1 Very active		Moderate improvement	No improvement	No improvement		

Protocol Code Number: SynAct-CS002

The DAS28 will be scored at baseline, after 2 weeks and 4 weeks treatment and at Visit 7.

21.3.4 Physician's Global Assessment of Disease Activity VAS ("Investigator Global VAS")

The physician's assessment of the subject's current disease activity on a 100 mm horizontal VAS. The extreme left end of the line should be described as "no disease activity" (symptom-free and no arthritis symptoms) and the extreme right end as "maximum disease activity." The efficacy assessor should complete this. Investigator Global VAS will be measured at screening, baseline, after 2 weeks and 4 weeks treatment and at Visit 7.

21.3.5 Patient's Global Assessment of Disease Activity VAS ("Patient Global VAS")

The subject's overall assessment of their current disease activity on a 100 mm horizontal VAS. The extreme left end of the line should be described as "no disease activity" symptom-free and no arthritis symptoms) and the extreme right end as "maximum disease activity" (maximum arthritis disease activity). Patient Global VAS will be measures at screening, baseline, after 2 weeks and 4 weeks treatment and at Visit 7.

21.3.6 Patient's Assessment of Pain VAS ("Patient Pain VAS")

The subject's assessment of his/her current level of pain on a 100 mm horizontal VAS. The extreme left end of the line should be described as "no pain" and the extreme right end as "unbearable pain." Patient Pain VAS will be measured at screening, baseline, after 2 weeks and 4 weeks treatment and at Visit 7.

21.3.7 Quality of Life and Physical Function

21.3.7.1 Functional Assessment of Chronic Illness Therapy-Fatigue (FACIT-Fatigue)

The FACIT-Fatigue assessment is a 13-item questionnaire with subjects scoring each item on a 5-point scale. The assessment was originally developed for chronic illnesses and is now validated for patients with RA. FACIT-Fatigue will be scored at baseline, after 2 weeks and 4 weeks treatment and at Visit 7.

21.3.7.2 Health Assessment Questionnaire – Disability Index (HAQ-DI)

HAQ-DI is a validated tool to evaluate physical function. It consists of 20 questions referring to 8 component sets: dressing/grooming, arising, eating, walking, hygiene, reach, grip, and activities. HAQ-DI will be scored at baseline, after 2 weeks and 4 weeks treatment and at Visit 7.

21.3.8 American College of Rheumatology Response Rates

The ACR (American College of Rheumatology) Criteria is a standard criterion to measure the effectiveness of various arthritis medications or treatments in clinical trials for RA.

The ACR response rates ACR20, ACR50, and ACR70 are defined as ≥20%, ≥50% and ≥70% improvement, respectively, in swollen and tender joint counts (SJC/TJC) and 3 of the following 5 assessments: Patient's Global Assessment of Disease Activity (see above), Physician's Global Assessment of Disease Activity (see above), Patient's Assessment of Pain (see above), Health Assessment Questionnaire (HAQ-DI, see above), and C-Reactive Protein (CRP).

21.4 Pharmacokinetic Assessments

The collection, processing, packing and shipping of PK, and cytokine samples are described in a separate Lab Manual for the study.

Protocol Code Number: SynAct-CS002

21.4.1 PK Sample Collection

Plasma PK samples for exposure-response analysis will be taken after 1, 2, 3- and 4-weeks treatment.

21.5 Cytokine Samples

Plasma samples for CXCL13, IL-1 β , IL-6, IL-10, and TNF- α analysis will be taken at baseline, after 2 weeks and 4 weeks treatment.

21.6 Biobanking

The following samples are kept at frozen storage in a biobank or similar, as applicable per country, during the study:

- Cytokines (CXCL13, IL-1β, IL-6, IL-10, and TNF-α), plasma
- PK, plasma

Analysis of all cytokines and PK will be performed at a central laboratory (Eurofins ADME BIOANALYSIS, [name], France). The samples will be sent and analyzed on a regular basis. All samples will be destroyed immediately after analysis. No samples are kept for future research.

Instructions for collection, processing, handling, and shipment of the frozen samples will be outlined in a laboratory manual.

The total volume of blood for biobanking is approximately 46 mL.

As France is part of the EU, the Data Protection Regulation and the Data Protection Act will be respected.

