15.3 Part 1 (main study only)

Following a successful screening evaluation, subjects who fulfill the enrollment criteria will be randomized in a 2:1 ratio in group A and B. One group will receive active treatment, and the other group will receive a placebo. Before randomization into group C/D (the same 2:1 ratio between active and placebo), the SC will look at blinded safety data from group A/B.

- Group A (min. 8 subjects): AP1189 dose 50 mg, once daily for 4 weeks (28 days) plus MTX (10-25 mg) weekly
- Group B (min. 4 subjects): placebo for 4 weeks (28 days) plus MTX (10-25 mg) weekly

SC Meeting

- Group C (min. 8 subjects): AP1189 dose 100 mg, once daily for 4 weeks (28 days) plus MTX (10-25 mg) weekly
- Group D (min. 4 subjects): placebo for 4 weeks (28 days) plus MTX (10-25 mg) weekly

Protocol Code Number: SynAct-CS002

15.3.1 Number of Subjects in Part 1

A minimum of 24 subjects is expected to complete Part 1 of the study. About 32 subjects are planned to be enrolled in accounting for discontinuation rate.

The rationale for the number of subjects required is outlined in the section on sample size determination.

15.4 Part 2

All subjects will be randomized into one design only, either design 1, 2, or 3 based on data from the interim analysis:

- Design 1: AP1189 dose 50 mg (min. 44 subjects) or placebo (min. 22 subjects), once daily for 4 weeks (28 days) plus MTX (10-25 mg) weekly
- Design 2: AP1189 dose 100 mg (min. 44 subjects) or placebo (min. 22 subjects), once daily for 4 weeks (28 days) plus MTX (10-25 mg) weekly
- Design 3: Continue with the same doses as in Part 1, in a 1:1:1 ratio (AP1189 50 mg (min. 22 subjects), AP1189 100 mg (min. 22 subjects) or placebo (min. 22 subjects)) plus MTX (10-25 mg) weekly

Following a successful screening evaluation, subjects who fulfill the enrollment criteria will be randomized accordingly.

15.4.1 Number of Subjects in Part 2

A minimum of 66 subjects in the main study is expected to complete Part 2 of the study, and 45 subjects in the sub-study. About 88 subjects are planned to be enrolled in the main study in accounting for discontinuation rate, and about 60 subjects in the sub-study.

The rationale for the number of subjects required is outlined in the section on sample size determination.

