23.1 General Considerations

Before breaking the treatment codes, all decisions on the evaluability of the data from each individual subject will be made and documented, and each subject will be assigned to the appropriate analysis data set. The following analysis sets will be used for the statistical analysis:

Safety: All subjects who received the study medication at least once, analyzed by received

treatment

PK: All the subjects who completed the study and did not have any protocol deviation or events

implying a bias for the PK evaluation

Efficacy: All randomized subjects who received the study medication at least once, analyzed by

randomized treatment (intention to treat). A second analysis of the primary efficacy endpoint, for robustness, will be performed for all randomized subjects who complete the

study without any major protocol violations (per protocol)

A Statistical Analysis Plan (SAP) describing the planned statistical analyses in detail, including interim analyses, will be prepared by CroxxMed, and validated by the sponsor prior to any unblinding of data.

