## Efficacy analysis

The HAQ-DI scale will be scored in accordance with Bruce and Fries, The Health Assessment Questionnaire (HAQ), *Clinical and Experimental Rheumatology*, 2005. Maska et al. summarize the scoring procedure as below (see https://onlinelibrary.wiley.com/doi/full/10.1002/acr.20620): "1) identify the highest subcategory score from each of the 8 categories. Adjust for use of aids/help by increasing the category score from 0 or 1 to a 2 if use of aids/help for that category (utilize table of companion aids/help for HAQ categories). If the category score is already a 2 or 3, no adjustment is made; 2) sum the category scores; and 3) divide the final sum by the number of categories answered to obtain the final HAQ score rounded to the nearest value evenly divisible by 0.125. Requires a minimum of 6 categories answered; if less, do not score."

The FACIT-Fatigue total subscale will be scored in accordance with http://www.ser.es/wp-content/uploads/2015/03/FACIT-F\_INDICE.pdf.

Change from baseline to week 4 (value at week 4 minus value at baseline) will be calculated for the following variables:

- CDAI
- DAS28
- HAQ-DI total score
- FACIT-Fatigue total subscale score
- number of swollen and/or tender joints (summarizing SJC and TJC)
- CXCL13
- IL-1β
- IL-6
- IL-10
- IL-6/IL-10 ratio
- TNF-α

In addition, percent change from baseline to week 4 (change from baseline as defined above divided by the baseline value) will be calculated for the following variables:

- CXCL13
- IL-1β
- IL-6
- IL-10
- IL-6/IL-10 ratio
- TNF-α

Indicators noting the following will be constructed, based on the above defined change in CDAI score from baseline to week 4:

- a 5-point decrease
- a 10-point decrease
- a 15-point decrease
- a 20-point decrease
- a 30-point decrease

Indicators noting a change in CDAI score will be constructed as follows:

- from severe (CDAI > 22) to moderate or lower (CDAI ≤ 22) at week 4 compared to baseline
- from severe (CDAI > 22) to low or remission (CDAI ≤ 10) at week 4 compared to baseline
- from severe (CDAI > 22) to remission (CDAI ≤ 2.8) at week 4 compared to baseline

Indicators noting a change in DAS28 will be constructed as follows:

- from > 3.2 to  $\leq$  3.2 at week 4 compared to baseline
- An indicator noting a change in DAS28 from high (DAS28 > 5.1) to moderate or lower (DAS28 ≤ 5.1) at week 4 compared to baseline

For the calculation of ACR response rates, indicators noting the following will be constructed:

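### Cytokine samples are assayed on a rolling basis and then destroyed, with no rule keeping a subject's visits in one run, so avoidable assay noise can enter the change from baseline

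*Protocol*

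**What the plan says.** Protocol 21.6 covers the plasma samples for the five cytokines and for PK, all analysed at one central laboratory. On storage it says: "The following samples are kept at frozen storage in a biobank or similar, as applicable per country, during the study". On timing and disposal: "The samples will be sent and analyzed on a regular basis. All samples will be destroyed immediately after analysis". Practical detail is left elsewhere: "Instructions for collection, processing, handling, and shipment of the frozen samples will be outlined in a laboratory manual". That manual is not among the documents.

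Cytokines are sampled at baseline, week 2 and week 4 (Protocol 21.5), and the week-4 visit falls 28 days, plus or minus one, after baseline (Protocol 20.1.6). The analysis is in SAP 3.6: "Change from baseline to week 4 (value at week 4 minus value at baseline) will be calculated for the following variables". The list that follows includes CXCL13, IL-1β, IL-6, IL-10, TNF-α and the IL-6/IL-10 ratio; percent change is derived for the same six. SAP 6.1.3 reports the mean change in each with a 95% confidence interval. Neither document mentions assay run in the analysis or says which samples must share one.

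**The concern.** A change from baseline is cleanest when both measurements come from the same run, because calibration error common to the run then largely cancels. If the two samples are assayed in different runs, each brings its own run error and the difference carries both. Percent change and the cytokine ratio are exposed in the same way.

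Frequent shipment makes this likely, since the baseline sample can be assayed and discarded before the week-4 sample exists. Normally a laboratory could repeat the pair together if a run looked shifted. Immediate destruction removes that option.

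At stake is the precision of the tertiary biomarker results. SAP Appendix 5 (revision history) shows that these changes will also be tabulated by CDAI decrease, by ACR response and in the quarter of subjects with the highest baseline CDAI, where numbers are smaller.

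**Working it through.** The plan states no shipment interval, run composition or assay precision, so there is no figure of its own to reproduce on this point. The only number in 21.6, about 46 mL of biobank blood, agrees with Table 6 (16 + 15 + 15 = 46) and does not bear on the matter.

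**Step 1: how many subjects are split.** Assume shipments every L days, all stored samples sent each time, one run per shipment, and enrolment unrelated to shipment dates. With samples 28 days apart, the share split is min(1, 28/L).

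| Assumed shipment interval | Share of subjects split |
|---|---|
| 28 days or less | about 100% |
| 30 days | 28/30 = 93% |
| 60 days | 28/60 = 47% |
| 91 days (quarterly) | 28/91 = 31% |
| 182 days | 28/182 = 15% |
| pooled by subject | 0% |

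**Step 2: what a split costs.** On the log scale, let s be the biological SD of the change, w the within-run SD and b the between-run SD.

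- Same run: variance = s² + 2w²
- Different runs: variance = s² + 2(w² + b²)

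All three inputs are assumptions: w = 0.08, b from 0.10 to 0.20, s from 0.3 to 0.7. Ratio of SDs, different runs to same run:

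| s | b = 0.10 | b = 0.15 | b = 0.20 |
|---|---|---|---|
| 0.3 | 1.09 | 1.20 | 1.33 |
| 0.5 | 1.04 | 1.08 | 1.14 |
| 0.7 | 1.02 | 1.04 | 1.08 |

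Middle case: same run 0.25 + 2(0.0064) = 0.2628; different runs 0.2628 + 2(0.0225) = 0.3078. The SD ratio is √(0.3078/0.2628) = 1.08, and 1 − 0.2628/0.3078 = 0.15, which is like losing 15% of subjects. Across the grid the loss runs from 4% to 44%.

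A second set of assumptions (between-run CV 5-20%, log-change CV 40-80%, no separate within-run term) gives an SD increase of 0.5% to 24%.

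**Step 3: only some subjects split.** The figures in Step 2 take every subject as split. With 31% split, the average variance in the middle case is 0.2628 + 0.31 × 0.045 = 0.2768, so the SD rises by √(0.2768/0.2628) − 1 = 2.6%.

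**Limits.** The SAP summarises raw pg/mL and percent change, so the log-scale result is an approximation. It also treats run errors as independent between subjects, although subjects sharing the same two runs share the error.

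**The case against.** The strongest objection is that the text permits split runs without prescribing them. A regular basis could mean quarterly, frozen storage allows a subject's visits to be held and sent together, and the unseen laboratory manual may already require this. That stands: a reader might infer from 21.6 that baseline and week-4 samples necessarily fall in different runs, and the documents do not support it. What remains is that the protocol sets no same-run rule while fixing a disposal rule that makes any split irreversible. Disposal after analysis could be read to include acceptance of the results and any repeat assay, but the word *immediately* sits badly with that reading.

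A second tempting inference is that run is tied to dose in Part 1, because the 100 mg stage follows the 50 mg stage: "Before randomization into group C/D (the same 2:1 ratio between active and placebo), the SC will look at blinded safety data from group A/B". This is weak. Each stage has its own concurrent placebo, the stated aim is AP1189 against placebo, and the arms of Part 2 (at least 66 of the 90 main-study completers) are randomised concurrently. A residual could arise if placebo subjects from the two stages are summarised together, but it would be confined to Part 1.

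Third, the size rests wholly on assumed assay figures, and the endpoints are tertiary and descriptive. Both statements are correct. They limit the point to a low-cost improvement. The interim analysis uses safety and CDAI only, so the choice of Part 2 design and the primary analysis are untouched.

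**Conclusion.** The point holds as a minor improvement. As written, 21.6 allows a subject's cytokine samples to be spread over several runs and then prevents repair. Between none and nearly all subjects are affected, depending on an interval the documents do not give. If all are split, the SD of the log change rises by 2-33% under the stated assumptions, with 8% in the middle case; at a quarterly interval the middle case falls to 2.6%. Run error unrelated to treatment adds noise and does not bias AP1189 against placebo.

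Because the same sentence covers PK, a reader might also infer that rolling PK results break the blind. The documents do not support that. Protocol 17.2 and 18.5.1 require CRO, sponsor and site staff to be blind to treatment, apart from the listed exceptions, and no section sends concentrations to them before code break. Evaluability is settled blind ("Before breaking the treatment codes, all decisions on the evaluability of the data from each individual subject will be made and documented"), and the PK set in Protocol 23.1 and SAP 3.2 is defined by completion and absence of deviations or events that would bias PK, not by concentration. Results held at an outside laboratory unblind nobody.

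Confirmation is still worthwhile because a concentration would be revealing. Samples precede the day's dose (Protocol 18.4), and phase 1 troughs were 46 ± 14 ng/ml at 50 mg and 100 ± 25 ng/ml at 100 mg (Protocol 11.3.1). With an assumed quantification limit of 1-20 ng/ml and normal values, a compliant 50 mg subject is measurable with probability 96.8% to 99.9%.

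**What to change.** In Protocol 21.6, and to match in the laboratory manual, state that:

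- cytokine samples stay frozen until the subject's set (baseline, week 2, week 4) is complete;
- all of a subject's cytokine samples are assayed in the same run;
- residual sample is destroyed only after the results have been accepted.

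This removes the 2b² term from the variance of the change, whatever the true assay precision. It remains compatible with the commitment to keep nothing for future research. It cannot recover samples already assayed and destroyed.

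The cost is a few weeks' longer frozen storage for the earlier samples, later cytokine results, and a wording change that has to be submitted, and approved where required, as an amendment under Protocol 26.1.1. Nothing in the interim analysis needs these results early.

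As a clarification only, confirm in the laboratory manual or data-transfer plan that PK concentrations are not released to blinded parties before code break.

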21.7 Total Volume of Blood

The total volume of blood to be collected from any subject during the trial will be up to 180 mL across 7 visits and will not exceed 36 mL at any one visit (see Table 6).

Table 6: Volume of Blood during the Trial

Protocol Code Number: SynAct-CS002

(mL blood)	Lab. Tests ¹	PK (plasma)	Cytokine samples (plasma)	CXCL13 samples (plasma)	Maximum per Visit
Visit 1, Screening Visit	36	0	0	0	36
Visit 2, Baseline Visit	17	0	5	5	27
Visit 3, 1. week treatment	15	4	0	0	19
Visit 4, 2. week treatment	17	4	5	5	31
Visit 5, 3. week treatment	15	4	0	0	19
Visit 6, 4. week treatment	17	4	5	5	31
Visit 7, final visit	17	0	0	0	17
Total during study	134	16	15	15	180

^{1:} Laboratory tests include a 15 mL blood sample for the analysis of hematology, biochemistry parameters, TSH, T4, T3, and serum β -HCG (pregnancy test at screening), as applicable, according to the study flowchart.

22 SAFETY

Adverse events will be monitored from the time that the subject gives informed consent and throughout the study, and will be elicited by direct, non-leading questioning or by spontaneous reports. Further details for AE reporting can be found in section 18.4.

Conditions that started before signing the informed consent and for which no symptoms or treatment are present until the first administration of study drug (e.g., seasonal allergy without acute complaints), are recorded as medical/surgical history.

22.1 Definitions

Adverse Events (AE): According to the International Conference of Harmonization (ICH), an AE is any untoward medical occurrence in a subject or clinical investigation subject administered a pharmaceutical product and which does not necessarily have a causal relationship with this treatment.

An AE can therefore be any unfavorable and unintended sign (including an abnormal laboratory finding), symptom, or disease temporally associated with the use of a medicinal or investigational product, whether or not considered related to the medicinal or investigational product. Pre-existing conditions which worsen during a study are to be reported as AEs.

Adverse Reaction (AR): All untoward and unintended responses to an investigational medicinal product related to any dose administered.

Serious Adverse Events (SAE): An SAE is any AE occurring at any dose that in the view of either the investigator or sponsor, results in any of the following outcomes:

Protocol Code Number: SynAct-CS002

- Results in death, or
- Is life threatening, that is any event that places the patient at immediate risk of death from the event as it occurred. It does not include an event that, had it occurred in a more severe form, might have caused death, or
- Requires inpatient hospitalization or prolongation of existing hospitalization, or
- Results in persistent or significant disability/incapacity, or
- Is a congenital anomaly/birth defect

Important medical events that may not result in death, be life-threatening, or require hospitalization may be considered a serious adverse event when, based upon appropriate medical judgment, they may jeopardize the subject and may require medical or surgical intervention to prevent one of the outcomes listed in this definition.

- Hospitalization is defined as any in-patient admission (more than 24 hours).
- Prolongation of hospitalization is defined as any extension of an in-patient hospitalization beyond the stay
 anticipated/required in relation to the original reason for the initial admission, as determined by the
 investigator or treating physician. Prolongation in the absence of a precipitating, treatment-emergent,
 clinical AE (i.e., not associated with the development of a new AE or worsening of a pre-existing condition)
 may meet criteria for "seriousness" but is not an adverse experience and thus is not subject to immediate
 reporting.
- Preplanned or elective treatments/surgical procedures should be noted in the subject's screening documentation. Hospitalization for a preplanned or elective treatment/surgical procedure should not be reported as an SAE unless there are complications or sequelae which meet the criteria for seriousness described above.

Planned hospitalizations that occur exclusively for study procedures must not be documented as SAEs.

Serious Adverse Reaction (SAR): Any serious adverse experience considered by the investigator to be related to the investigational product is a SAR.

Suspected Unexpected Serious Adverse Reactions (SUSARs): SUSARs are serious reactions that are not listed in the IB and that the investigator identifies as related to the investigational product or procedure.

